6.3. REPEATS, UNSCHEDULED VISITS AND EARLY TERMINATION DATA

In order to control for the potential progressive change in tau deposition over time, cognitively impaired subjects for whom death did not occur within nine months of the ¹⁸F-AV-1451 PET scan were given the opportunity to undergo a second ¹⁸F-AV-1451 PET scan and continue in the protocol at the Sponsor's discretion. If the subject agreed to a second ¹⁸F-AV-1451 PET scan, screening assessments were not repeated with exception of any updates to the medical history/concurrent medications and an updated neurological disease diagnosis (according to best available information) which were collected at the time of the second ¹⁸F-AV-1451 PET imaging visit. If the subject subsequently came to autopsy, the data (neurological disease diagnosis and ¹⁸F-AV-1451 PET scan) from the second ¹⁸F-AV-1451 PET imaging visit

Document: \\quintiles.net\enterprise\Apps\sasdata\SASa\sas\AVID\18F-AV-1451\Biostatistics\Documentation\SAP\Avid_18F-AV-1451-A16_SAP_Final_v1.0_20180815.docx

Author: XXXXXXXXXX	Version Number: Final, v1.0
	Version Date: 15Aug2018
	Reference: CS_WI_BS005

Template No: CS_TP_BS016 – Revision 3
Effective Date: 01May2012

Copyright © 2012 Quintiles Transnational Corp. All rights reserved.

The contents of this document are confidential and proprietary to Quintiles Transnational Corp. Unauthorized use, disclosure or reproduction is strictly prohibited.

(nearest to time of death) will be used in the analyses. Cognitively normal (unimpaired) subjects were not required to undergo repeat scans, even if death occurred more than nine months after the ¹⁸F-AV-1451 PET scan, because cortical tau deposition is expected to occur very slowly, if at all, in such subjects. That is, cognitively normal subjects remained eligible for autopsy, regardless of time from first or second scan to autopsy. The safety analyses will include data from all scans.

This study does not accommodate unscheduled visits and no data will be collected at the time of an early termination beside the date and reason for discontinuation.

Listings will include scheduled, repeat, and early discontinuation data.

6.4. WINDOWING CONVENTIONS

No visit windowing will be performed for this study.

6.5. SOFTWARE VERSION

All analyses will be conducted using SAS® version 9.4 or higher.

7. STATISTICAL CONSIDERATIONS

7.1. SAMPLE SIZE JUSTIFICATION AND TRIAL STOPPING CRITERIA

Assuming sensitivity/specificity of approximately 80%, a minimum of 14 autopsy cases in each of the TS groups (pathological positive or negative as defined in Table 2 and Table 3) is required for the lower bound of the two-sided 95% confidence interval (CI) to be > 50% for each individual reader.

The Sponsor is blinded to the pathological results (TS) until after the study is completed and the database is locked. Therefore, in order to ensure that an adequate number of subjects were recruited and came to autopsy for each TS group, the Sponsor assumed that subjects diagnosed on clinical grounds as having dementia due to AD are TS positive and subjects diagnosed as having no cognitive impairment (cognitively normal) are TS negative. Based on these assumptions, the study sample size requirement and trial stopping criteria were to be deemed as having been met when:

- the number of subjects diagnosed as having impairment due to AD that came to autopsy was greater than or equal to 14, AND
- the number of subjects diagnosed as having no cognitive impairment that came to autopsy was greater than or equal to 14

The Sponsor recognizes that there might have been some error in clinical diagnosis such that some subjects diagnosed clinically as having impairment due to AD may have non-AD pathology, or limited amounts of AD tau pathology, and thus be TS negative, and less often, subjects considered clinically

Document:	\\quintiles.net\enterprise\Apps\sasdata\SASa\sas\AVID\18F-AV-1451\Biostatistics\Documentation\SAP\Avid_18F-AV-1451-A16_SAP_Final_v1.0_20180815.docx		
Author:	██████████	Version Number:	Final, v1.0
		Version Date:	15Aug2018
Template No:	CS_TP_BS016 – Revision 3	Reference:	CS_WI_BS005
Effective Date:	01May2012		

normal may have AD pathology and thus be TS positive. However, given the excess frequency of cases with AD diagnoses relative to clinically normal subjects recruited in this trial population, any diagnosis errors will likely help ensure a minimum of 14 TS negative subjects without jeopardizing the criterion for TS positive subjects.

In addition to the above subjects diagnosed as clinically normal or AD patients, it was expected that approximately 10-15 subjects with non-AD impairment would be enrolled and come to autopsy in this trial. However, the proportion of these subjects that will have TS positive/negative AD tau pathology is very difficult to predict and will depend on the precise cases enrolled. Thus, it was not expected that the clinical profile of these cases would be useful in estimating when a sufficient number of cases had occurred in each TS group.

In accordance with protocol amendment 2, the actual number of cases that met the TS positive and TS negative criteria at autopsy were determined in an unblinded fashion using the neuropathology consensus panel results by an independent statistician who is not an employee of the Sponsor and who is not involved in the conduct and analysis of the study. Because the number of cases in this study were too large to review in a single session, this panel met periodically during the course of the trial and reviewed the cases in batches. After the third consensus panel meeting (held in May 2018), the independent statistician reviewed the consensus panel data and notified the Sponsor that the stopping criteria were met (i.e., at least 14 cases in each of the TS positive and negative categories had come to autopsy).

By the time the independent statistician notified the sponsor that the stopping criteria were met, more than 14 subjects diagnosed as having no cognitive impairment and more than 14 subjects diagnosed as having impairment due to AD had come to autopsy. Hence, both set of stopping criteria were met after the third consensus panel meeting that was held in May 2018.

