8.6. Sample Size Calculation and Trial Stopping Criteria

Assuming sensitivity/specificity of approximately 80%, a minimum of 14 autopsy cases in each of the truth standard groups (pathological positive or negative) is required for the lower bound of the two-sided 95% CI to be > 50% for each individual reader. The sponsor is blinded to the pathology results (truth standard) until after the study is completed and the database is locked. Therefore, in order to ensure that an adequate number of subjects are recruited and come to autopsy for each truth standard group, the sponsor will assume that subjects diagnosed on clinical grounds as having dementia due to AD will be truth standard positive, subjects diagnosed as having no cognitive impairment (cognitively normal) will be truth standard negative. Based on these assumptions, the study sample size requirement and trial stopping criteria will be deemed to have been met when

- the number of subjects diagnosed as having impairment due to AD that have come to autopsy, is greater than or equal to 14, AND
- the number of subjects diagnosed as having no cognitive impairment that have come to autopsy is greater than or equal to 14

The sponsor recognizes that there may be some errors in clinical diagnosis such that some patients diagnosed clinically as having impairment due to AD may have a nonAD pathology, or limited amounts of AD tau pathology, and thus be truth standard negative, and, less often, subjects considered clinically normal may have AD pathology and be truth standard positive. However, given the excess frequency of cases with AD diagnoses relative to clinically normal subjects already recruited in this trial population, any diagnostic errors will likely help ensure a minimum of 14 truth standard negative subjects without jeopardizing the criterion for truth standard positive subjects.

In addition to the above subjects diagnosed as clinically normal or AD patients, it is expected that approximately 10-15 subjects with nonAD impairments will be enrolled and come to autopsy in this trial. However, the proportion of these that will have truth standard positive/negative AD tau pathology is very difficult to predict and will depend on the precise cases enrolled. Thus, it is not expected that these cases will be useful in

estimating when a sufficient number of cases have occurred in each truth standard group and are not employed in the stopping criteria.

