5.4.1. FULL ANALYSIS SET #1

The FAS #1 (FAS1) will include all SAF subjects (refer to Section 5.2) recruited under this protocol that:

- came to autopsy, *including* the Front-Runner Cohort (i.e., including the first three subjects who came to autopsy),
- had valid and evaluable PET data (refer to Section 3.2), and
- had valid and interpretable autopsy specimens (refer to Section 3.3), where interpretability will be assessed for the Braak Stage.

This analysis set will be used to summarize the consensus panel’s assessment of each TS (refer to Section 15.1), conduct supportive analyses to the first primary efficacy analysis (refer to Section 15.1.1) and secondary analysis of majority of readers versus the NFT Score TS (15.2.1) as well as to conduct the exploratory efficacy analysis exception of the logistic regression model for the NIA-AA autopsy diagnosis TS (refer to Section 15.3). Data will be presented according to the individual reader’s interpretation of the ¹⁸F-AV-1451 PET image (see Section 3.2 and APPENDIX 1), majority of readers’ interpretation of the ¹⁸F-AV-1451 PET image (see Section 3.2 and APPENDIX 1) or by most recent neurological disease diagnosis, as appropriate.

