5.5.2. EFFICACY ANALYSIS SET #2

The EFF #2 (EFF2) will include all SAF subjects (refer to Section 5.2) recruited under this protocol that:

- came to autopsy *after* the Front-Runner Cohort (i.e., excluding the first three subjects who came to autopsy),
- had valid and evaluable PET data (refer to Section 3.2), and
- had valid and interpretable autopsy specimens (refer to Section 3.3) , where interpretability will be assessed for the NIA-AA autopsy diagnosis.

This analysis set will be used to conduct the second primary efficacy analysis (refer to Section 15.1.2) and majority of readers secondary efficacy analysis for the NIA-AA autopsy diagnosis (refer to Section 15.2.1). Summaries will be presented according to the individual reader’s or majority of readers’ interpretation of the ¹⁸F-AV-1451 PET image (see Section 3.2 and APPENDIX 1), as appropriate.

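### Does the stopping count of 14 cases per truth-standard group have to be re-confirmed within the two primary efficacy sets?

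*SAP*

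**What the plan says.** SAP 7.1 assumes sensitivity and specificity of about 80% and takes 14 as the minimum per TS group, the groups being "pathological positive or negative as defined in Table 2 and Table 3". Table 2 is the NFT score standard for the first primary analysis, and Table 3 is the NIA-AA standard for the second.

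Two stopping counts appear:

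- **Clinical diagnosis.** Protocol 8.6 requires at least 14 subjects with impairment due to AD and also that "the number of subjects diagnosed as having no cognitive impairment that have come to autopsy is greater than or equal to 14".
- **Pathology.** SAP 7.1 says an independent statistician used the consensus panel results and told the sponsor, after the May 2018 panel meeting, that "at least 14 cases in each of the TS positive and negative categories had come to autopsy". It adds that by then the autopsied cases included "more than 14 subjects diagnosed as having no cognitive impairment and more than 14 subjects diagnosed as having impairment due to AD".

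The analysis sets are narrower. SAP 5.5.1 and 5.5.2 define EFF1 and EFF2 as "excluding the first three subjects who came to autopsy" and require evaluable PET. Under SAP 3.2 a scan is unevaluable if at least three of the five readers say so for the same reason. SAP 3.4 states that the statistician saw neither images nor reads. FAS1 (SAP 5.4.1) is defined as "including the first three subjects who came to autopsy".

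**The concern.** The number that closed the cohort is not stated in terms of the sets on which the two primary hypotheses are tested. There are three gaps:

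1. Front-runners are by definition the first to reach autopsy, and nothing removes them from the count. SAP 5.4.1 says of FAS1, the set that keeps them, "This analysis set will be used to summarize the consensus panel", going on to that panel's assessment of each TS. They may therefore be in the data the statistician reviewed.
2. Reader-unevaluable scans could not have been removed by someone blinded to the reads.
3. One count is reported for two standards. The NIA-AA standard also uses Thal and CERAD scores, so a case can be positive under one and negative under the other.

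The provenance is also unclear. SAP 7.1 introduces the step with "In accordance with protocol amendment 2, the actual number of cases that met the TS positive and TS negative criteria at autopsy", yet section 8.6 of the supplied Amendment 2 contains no independent-statistician count.

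At stake is power. If a tested set holds fewer than 14 cases in a group, the planned minimum was not reached and each reader's chance of success may be lower than planned. The same count was also the stated ground in SAP 3.1 for keeping outside cases out of the main efficacy sets.

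**Working it through.** **Inputs.** Assumed rate 80%, two-sided 95% Wilson interval, threshold 50%, minimum 14 (SAP 7.1, 7.5.1, 15.1.1). Three front-runners (SAP 3.1). The documents give neither the actual TS counts nor the number of reader-unevaluable scans, so the losses below are assumptions.

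**Reproducing 14.** With p = x/n and z = 1.96,

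lower bound = [p + z²/(2n) − z·√(p(1−p)/n + z²/(4n²))] / (1 + z²/n).

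For 11/14: [0.7857 + 0.1372 − 1.96·√(0.01203 + 0.00490)] / 1.2744 = 0.6679/1.2744 = 52.41%, a pass. Taking the largest whole count not above 80%, 10/13 gives 49.74%, 9/12 gives 46.77% and 8/11 gives 43.44%, all failures. So 14 is reproduced, with no slack at an observed rate near 80%.

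**What a shortfall would cost.** The chance that one reader passes one measure is the binomial probability of reaching the smallest passing count:

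| n in TS group | Smallest passing count | Wilson lower bound | Pass chance, true 80% | Pass chance, true 90% |
|---|---|---|---|---|
| 11 | 9 | 52.30% | 61.7% | 91.0% |
| 12 | 10 | 55.20% | 55.8% | 88.9% |
| 13 | 11 | 57.77% | 50.2% | 86.6% |
| 14 | 11 | 52.41% | 69.8% | 95.6% |
| 15 | 12 | 54.81% | 64.8% | not computed |
| 16 | 12 | 50.50% | 79.8% | not computed |
| 17 | 13 | 52.74% | 75.8% | not computed |

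If a group's count was exactly 14 and all three front-runners fell in it, 14 − 3 = 11 remain and the chance moves from 69.8% to 61.7%. Sensitivity and specificity use different cases, so for one reader passing both measures the chance is 0.698 × 0.698 = 48.7% at 14 and 14, and 0.617 × 0.698 = 43.1% at 11 and 14. The lowest value in this range is 0.502 × 0.698 = 35.0%, at 13 and 14.

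The pattern is a saw-tooth: 11 does better than 13, and 14 better than 15. Much of any apparent drop comes from discreteness and not from information lost.

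**When front-runners alone could cause it.** A count of 14 + 3 = 17 or more in a group guarantees 14 after their removal. A shortfall from this source needs a count of 16 or fewer and enough of the three in that group. Neither is documented.

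**Does a smaller n loosen the test?** At a true 50%, the pass chance for one reader on one measure is 2.87% at n = 14, against 3.27%, 1.93% and 1.12% at 11, 12 and 13. There is no material inflation.

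**What is already excluded.** Tissue the panel rates not evaluable in both hemispheres yields no TS (SAP 3.3). Scans the core laboratory finds invalid are not followed to autopsy (Protocol 8.2). Only front-runners and reader-unevaluable scans remain at issue.

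**Where the counts will appear.** By SAP 7.5.1 the sensitivity denominator is TP + FN and the specificity denominator is FP + TN. In EFF1 and EFF2 these are the TS-positive and TS-negative numbers under Tables 2 and 3, apart from any individual read that is missing.

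**The case for a change.** The best case for acting is that one count carried two decisions. It ended new autopsies (Protocol 8.6), and it kept outside cases out of the efficacy sets (SAP 3.1). Such a count should refer to the sets being tested, and one clarifying sentence with a yes/no recount before database lock looks cheap. The surplus by clinical diagnosis does not answer this fully, since the SAP concedes diagnostic error and those counts carry the same missing exclusions.

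Part of this stands: the statement in SAP 7.1 does not confirm 14 per group in EFF1 and EFF2, and on the documents reader-unevaluable scans could not have been removed. The rest is weaker.

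- SAP 7.1 does name the standards when it defines the TS groups. What is missing is a separate statement for each.
- That front-runners were counted is an inference from a later descriptive use of FAS1, not something the text says.
- The SAP is written to Amendment 3 (SAP 1), which was not among the documents reviewed, and SAP 3.1 cites protocol section 8.6 for this step. The governing rule may be there, and the mention of Amendment 2 may be a slip in citation.
- The recount is not free. It would pass reader-declared evaluability to a statistician who holds unblinded pathology and is deliberately kept from the reads.

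**Conclusion.** No change to the plan. This is a gap in what one sentence confirms, with no demonstrated shortfall behind it. Stopping was declared in May 2018, before the SAP of 15 August 2018, so redefining the minimum now would alter no enrolment, analysis set, test or conclusion.

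A shortfall would cost power and would not bias the result, because success is read from the intervals obtained at whatever n exists. It would also be visible: SAP 9 reports membership of each set with reasons for exclusion, SAP 15.1.1 and 15.1.2 list subjects by TS status, and the primary denominators give the counts. The outside cases are not lost either, since SAP 3.1 plans supportive analyses with them.

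The documents make a large deficit unlikely without excluding a small one. More than 14 subjects in each clinical group had come to autopsy, 10 to 15 further non-AD cases were expected, about 80 autopsies were planned, and autopsies under way at stopping were added. The illustrative cost, 69.8% to 61.7% for one reader on one measure (50.2% at the least favourable n in the range), assumes a true rate of 80%, a count of exactly 14, and all the loss in one group. At a true 90% the chance stays at 86.6% or higher for n from 11 to 14.

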7.2. MULTICENTER STUDIES

This study was conducted by multiple investigators at multiple centers. However, there are no plans to perform a formal analysis of homogeneity across centers.

7.3. MISSING DATA

Missing efficacy and safety data will not be imputed with the exception of missing AE severity and missing AE relationship to study medication/procedure (refer to Sections 16.1.1.1, 16.1.1.2, and 16.1.1.3, respectively). Missing or partial AEs and medications dates and/or time will be handle as described in APPENDIX 2.

It is possible that for some cases, only half of the brain tissues was available for pathological analysis while the whole brain ¹⁸F-AV1451 PET scan images were available for visual reads. For these cases, only the visual reads from corresponding side of brain will be used for efficacy analyses.

7.4. HYPOTHESES TESTING AND MULTIPLE COMPARISONS/ MULTIPLICITY

For the primary analysis of the first primary efficacy endpoint (refer to Section 15.1.1), the hypothesis to be tested is that for at least the same 3 out of 5 independent readers, the lower bound of the two-sided 95% CI for both sensitivity and specificity of ¹⁸F-AV-1451 PET reading interpretations will be $\geq 50\%$.

For the primary analysis of the second primary efficacy endpoint (refer to Section 15.1.2), the hypothesis to be tested is also that for at least the same 3 out of 5 independent readers, the lower bound of the two-sided 95% CI for both sensitivity and specificity of ¹⁸F-AV-1451 PET reading interpretations will be $\geq 50\%$.

This trial will be considered as successful if both primary efficacy analyses reach statistical significance at a two-sided significance level of 0.05.

All other efficacy endpoints (refer Sections 15.2.1, 15.2.2, and 15.3) will be tested without multiplicity adjustments and nominal p-values will be provided. Although nominal p-values will be provided for the secondary efficacy endpoints, the hypothesis to be tested for these endpoints are:

- The majority read results will have the lower bound of the two-sided 95% CI $\geq 55\%$ for both sensitivity and specificity for detection of tau neurofibrillary pathology that corresponds to NFT score of B3,
- The majority read results will have the lower bound of the two-sided 95% CI $\geq 55\%$ for both sensitivity and specificity for detection of a pattern of ¹⁸F-AV-1451 neocortical uptake that corresponds to a high levels of AD neuropathologic change as defined by NIA-AA criteria, and
- The observed kappa values are ≥ 0.64 and the lower bound of the two-sided 95% CIs are ≥ 0.55 for the inter-reader agreement among readers.

No statistical testing will be carried out for disposition and withdrawal (refer to Section 9), demographic or other baseline characteristics (refer to Section 10), medical/surgical history (refer to Section 11), concurrent diseases/conditions (refer to Section 11), prior and concomitant medications (refer to Section 12), exposure to ¹⁸F-AV-1451 (refer to Section 14), other efficacy endpoint (refer to Section 15.4), and all safety outcomes (refer to Section 16).

7.5. STATISTICAL MODELS

The following general statistical models will be used in the analysis of the primary, secondary, and exploratory efficacy endpoints.

7.5.1. SENSITIVITY, SPECIFICITY, POSITIVE AND NEGATIVE PREDICTIVE VALUES, AND LIKELIHOOD RATIOS

The following table contains terms used to define sensitivity, specificity, accuracy, positive predictive value (PPV), negative predictive value (NPV), likelihood ratio positive (LR+) and likelihood ratio negative (LR-):

Document:	\\quintiles.net\enterprise\Apps\sasdata\SASa\sas\AVID\18F-AV-1451\Biostatistics\Documentation\SAP\Avid_18F-AV-1451-A16_SAP_Final_v1.0_20180815.docx		
Author:	XXXXXXXXXX	Version Number:	Final, v1.0
		Version Date:	15Aug2018
Template No:	CS_TP_BS016 – Revision 3	Reference:	CS_WI_BS005
Effective Date:	01May2012		

Diagnostic Test: ¹⁸ F-AV-1451 PET Scan Read Result	Truth Standard	
	Positive	Negative
Positive	True Positive (TP)	False Positive (FP)
Negative	False Negative (FN)	True Negative (TN)

The sensitivity, which evaluates how good a test is at detecting a positive disease, will be calculated as:

$$100 \times \frac{TP}{TP + FN}$$

The specificity, which estimates how likely subjects without the disease can be correctly ruled out, will be calculated as:

$$100 \times \frac{TN}{FP + TN}$$

The accuracy, which evaluates the overall proportion of observed agreement, will be calculated as:

$$100 \times \frac{TP + TN}{TP + FN + FP + TN}$$

The PPV, which is the proportion of positive test results that are true positives, will be calculated as:

$$100 \times \frac{TP}{TP + FP}$$

The NPV, which is the proportion of subjects with a negative test result who are correctly diagnosed, will be calculated as:

$$100 \times \frac{TN}{FN + TN}$$

The 95% CIs provided for specificity, sensitivity, accuracy, PPV and NPV will be based on the Wilson score method (Wilson 1927; Newcombe 1998).

The LR+, which is true positive rate divided by the false positive rate, will be calculated as:

$$\frac{\textit{sensitivity}}{1 - \textit{specificity}}$$

The LR-, which is the false negative rate divided by the true negative rate, will be calculated as:

$$\frac{1 - \textit{sensitivity}}{\textit{specificity}}$$

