15.1. PRIMARY EFFICACY

15.1.1. PRIMARY EFFICACY ANALYSIS #1

For the primary efficacy analysis #1, the diagnosis performance (sensitivity/specificity) of 5 independent readers' interpretation of ante-mortem ¹⁸F-AV-1451 PET scan images (AD+/AD++ or AD-; refer to Section 3.2) for detection of a pattern of ¹⁸F-AV-1451 PET neocortical uptake that corresponds to NFT score B3 (Hyman et al., 2012; Montine et al., 2012; refer to Section 3.3) at autopsy will be evaluated.

¹⁸ F-AV-1451 PET Scan Read Result	Autopsy NFT Score TS	
	NFT Score B3 (True Positive)	NFT Score B0, B1 or B2 (True Negative)
AD+/AD++: ¹⁸ F-AV-1451 Neocortical Uptake Consistent with AD Pattern	TP	FP
AD-: ¹⁸ F-AV-1451 Neocortical Uptake Not Consistent with AD Pattern	FN	TN

The sensitivity and specificity along with their two-sided 95% CI (based on the Wilson score method) will be calculated for each of the five readers. The first primary efficacy analysis will be considered to be met if for at least the same 3 out of 5 readers, the lower bound of the 95% CI for both sensitivity and specificity are $\geq 50\%$ (i.e., statistically significant at two-sided significance level of 0.05).

The accuracy, PPV, NPV, LR+ and LR- of the ¹⁸F-AV-1451 PET imaging classification for each of the five readers relative to the autopsy NFT score TS will be also calculated. Two-sided 95% CIs (based on the Wilson score method) will be provided for the accuracy, the PPV and NPV.

Additionally, the number and percentage of subjects for each Braak stage and NFT stage will be provided for each hemisphere overall and by most recent neurological disease diagnosis. The number and percentage of subjects in each highest hemisphere/stain NFT score and autopsy NFT score TS will be summarized overall and by most recent neurological disease diagnosis. A listing of subjects who are autopsy NFT score TS positive and TS negative will be provided including the same information as well as the readers' interpretation of the ¹⁸F-AV-1451 PET scan image(s).

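### SAP 7.5.1 puts sensitivity and specificity on a 0–100 scale but subtracts them from 1 in the likelihood-ratio formulas, so read literally both ratios come out negative

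*SAP*

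**What the plan says.** SAP Section 7.5.1 gives calculation rules for seven measures. Five of them (sensitivity, specificity, accuracy, PPV and NPV) carry an explicit factor of 100. In particular:

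- sensitivity = 100 × TP/(TP + FN)
- specificity = 100 × TN/(FP + TN)

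The two likelihood ratios follow. Each has a definition in words and then a formula that reuses the names just defined:

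- "The LR+, which is true positive rate divided by the false positive rate", with formula sensitivity/(1 − specificity)
- "The LR-, which is the false negative rate divided by the true negative rate", with formula (1 − sensitivity)/specificity

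No rescaling is stated there or elsewhere in the SAP, and the protocol does not mention likelihood ratios.

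These are planned outputs. SAP 15.1.1 lists "The accuracy, PPV, NPV, LR+ and LR- of the" PET classification for each of the five readers against the NFT truth standard. SAP 15.1.2 does the same against the NIA-AA standard, and SAP 15.2.1 does so for the majority read against both.

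**The concern.** The complement of a quantity on a 0–100 scale is 100 minus that quantity, not 1 minus it. With the definitions printed a few lines above them, the formulas do not return a ratio of two rates. They return a negative number that carries almost no diagnostic information.

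The section is the specification that programs are written and checked against. A programmer has to notice the mismatch and correct it without instruction. A half-correction would be harder to see than a negative value: a percentage numerator over a proportion denominator gives a positive result that is 100 times too large.

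The main efficacy sets would hold 24 such values: 5 readers × 2 truth standards × 2 ratios = 20, plus the majority read × 2 standards × 2 ratios = 4. The supportive analyses (SAP 15.1.3 and 15.2.3) and the subgroup analyses of the primary endpoints (SAP 15.1.4) repeat them.

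**Working it through.** **Inputs.** The definitions and formulas come from SAP 7.5.1. The planning value and minimum group size come from SAP 7.1: "Assuming sensitivity/specificity of approximately 80%, a minimum of 14 autopsy cases in each of the TS groups". The documents state no likelihood-ratio value, so the only figure to reproduce is the 14.

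**The plan's own figure.** I used the two-sided 95% Wilson lower bound, with the whole-number count at or just below 80%:

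- 10/13 gives 49.7%
- 11/14 gives 52.4%

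So 14 per group reproduces. This has no bearing on the likelihood ratios except to fix a realistic operating point.

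**The formulas as printed, on the SAP's 0–100 scale, against the same ratios on the proportion scale.**

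At 80/80, as printed:

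- LR+ = 80/(1 − 80) = 80/(−79) = −1.013
- LR− = (1 − 80)/80 = −79/80 = −0.988

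At 80/80, as proportions:

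- LR+ = 0.80/0.20 = 4.00
- LR− = 0.20/0.80 = 0.25

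| Sensitivity / specificity | LR+ as printed | LR+ correct | LR− as printed | LR− correct |
|---|---|---|---|---|
| 50 / 50 | −1.020 | 1.00 | −0.980 | 1.00 |
| 11/14 for both | −1.013 | 3.67 | −0.987 | 0.273 |
| 80 / 80 | −1.013 | 4.00 | −0.988 | 0.25 |
| 90 / 75 | −1.216 | 3.60 | −1.187 | 0.133 |
| 100 / 100 | −1.010 | undefined (zero denominator) | −0.990 | 0 |

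Replacing 1 by 100 gives the same values as the proportion scale: 80/(100 − 80) = 4.00 and (100 − 80)/80 = 0.25.

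**Why dropping the sign does not rescue the values.** As printed, LR+ = −sensitivity/(specificity − 1) and LR− = −(sensitivity − 1)/specificity. When both measures are well above 1, each is close to −sensitivity/specificity. A coin-tossing reader (50/50) and a perfect reader (100/100) therefore get nearly the same pair of numbers.

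**How general this is.** The printed LR+ is negative when specificity exceeds 1 and sensitivity exceeds 0. The printed LR− is negative when sensitivity exceeds 1 and specificity exceeds 0. Both are therefore negative whenever sensitivity and specificity both exceed 1%. With 14 cases per group there are 15 × 15 = 225 possible combinations of TP and TN. Both ratios are negative in all 14 × 14 = 196 with at least one true positive and one true negative. In the other 29, sensitivity or specificity is zero.

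**The half-correction.** At 80/80, a percentage over a proportion gives LR+ = 80/(1 − 0.80) = 400 instead of 4.00.

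**The case against.** The best defence is that the section explains itself. Each formula is introduced by a correct definition in words, and a ratio of two rates cannot be negative, so a competent programmer knows what to compute. The slip can also be read as loose notation. The SAP writes its thresholds with a percent sign, and Protocol Section 8.2.1 describes sensitivity and specificity as proportions of cases. If the factor of 100 is taken to mean 100%, then 1 − 80% = 20% and the standard formulas are right.

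Part of this stands. The intent is clear, a literal result would be conspicuous, and no stated figure is wrong. The percent-sign reading does not rescue the text, though. Section 7.5.1 prints 100, not 100%, whereas SAP 15.2.2 and 15.3 do write 100% where that is meant. Correct words beside a formula show what was intended, but they do not make the formula correct.

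A reader might also infer that the likelihood ratios matter especially because they are the only accuracy summaries, apart from sensitivity and specificity, that do not depend on the recruited case mix. The documents do not support this:

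- SAP 15.3 also reports the ROC area for SUVr, and correct-classification percentages separately for truth-standard positive and negative subjects. None of these depends on the positive-to-negative split.
- LR+ and LR− are functions of sensitivity and specificity, which are reported beside them, so they add no independent information.
- They are free of prevalence, not of case mix in general. If specificity differs between B0 and B2 cases, they shift with the balance of those cases in the negative group.

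**Conclusion.** The inconsistency is real but minor. It rests only on substituting the section's own definitions into its own formulas. At the planning value the literal results are −1.01 and −0.99 where 4.00 and 0.25 are meant, and the sign is wrong for any sensitivity and specificity above 1%.

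The effect stops at descriptive outputs. SAP 15.1.1, 15.1.2 and 15.2.1 plan no confidence interval for LR+ or LR−. SAP 7.4 attaches no hypothesis to them, and success depends on the Wilson lower bounds for sensitivity and specificity. A reader might infer that the diagnostic conclusions are at risk, but nothing in the documents supports that. Nor do the documents show that any output was actually produced with the literal formulas.

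**What to change.** Either of two equivalent changes in SAP 7.5.1 is enough:

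- Replace 1 by 100: LR+ = sensitivity/(100 − specificity) and LR− = (100 − sensitivity)/specificity.
- Define both ratios from the counts: LR+ = [TP/(TP + FN)]/[FP/(FP + TN)] and LR− = [FN/(TP + FN)]/[TN/(FP + TN)].

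The second is safer because it does not depend on the scale used elsewhere. The cost is two lines of text, with no change to data, analysis sets, decision rules or sample size. A separate matter that could be settled in the same edit is that the corrected LR+ has a zero denominator when specificity is 100%. The SAP gives no rule for displaying that case, and one sentence would supply it.
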